## **8.6. Reporting to the Sponsor**

All SAEs and SUSARs must be forwarded the Imperial College Joint Research Office within 24 hours of the Investigator learning of its occurrence.

## **8.7. Reporting to Vifor Pharma Drug Safety**

All SAEs that are considered possibly, probably or definitely related to the study drug must be forwarded to Vifor Pharma Pharmacovigilance by fax or e-mail within 1 business day of learning of the event:

[contact]  
[[contact]](mailto:[contact])

## **8.8. Follow up of adverse events**

All adverse events that are still ongoing at the end of the study will be followed up until resolution.

# **9. DOCUMENTATION OF DATA**

## **9.1. Data collection**

The data collection tool for this study will be electronic case report forms (eCRFs). Case report forms (CRFs) will be completed for each subject and will contain study data which are verifiable to the source data (i.e., original recordings, laboratory reports, and subject records). In addition, all source data should be attributable (signed and dated).

Only the Investigator and authorized co-workers are entitled to make entries on the CRF. Concomitant medications may be entered as they appear in the participant's record or as per local standards (generic or trade names may be entered).

It is the responsibility of the Investigator to ensure that the CRFs are kept up-to-date so that they always contain the latest observations on the subjects enrolled.

Laboratory values outside the normal range will be commented upon by the Investigator. Other data than those requested by this protocol may be recorded as "additional data" in the comments section of the case report form; the clinical significance of any additional data should be described.

## **9.2. Data monitoring**

The Sponsor is responsible for ensuring that the study is monitored appropriately in order to ensure compliance with GCP and local regulatory guidelines. The monitor will check the completeness of medical records, verify the accuracy of entries in the CRF, and ensure adherence to the protocol and compliance with local regulatory requirements.

# **10. STATISTICS AND DATA ANALYSIS**

This is a proof-of-concept study, thus the sample size has been chosen with respect to safety (in terms of exposure to the drug and investigations) and feasibility (patient population) and with the aim of measuring effect size. We would expect that a sample size of 60 will be sufficient to detect clinically meaningful changes in cardiopulmonary exercise end-points, NT-pro-BNP and quality of life in the direction consistent with benefit.

The null hypothesis is that iron replacement has no effect on cardiopulmonary performance in patients with iron deficiency and IPAH, with a two-sided alternative that iron replacement changes cardiopulmonary performance in patients with iron deficiency and IPAH.

For the cardiopulmonary exercise tests, if a 12-weekly drop-out rate of 10% and standard deviation of 5 ml/min/kg for peak VO2 we would have 80% power to detect a mean change of 1.94 ml/min/kg at a significance level of alpha=0.05 using a paired analysis (cf 2.2ml difference in FERRIC-HF with 35 patients). Other pre-specified secondary endpoints will be change in CPET at 2 weeks, change in cardiac output at 12 weeks, and change in 6 minute walk distance and circulating biochemical markers at 12 weeks. A full statistical analysis plan will be developed for each endpoint, using linear mixed models for analysis of the crossover data. Primary analysis will be intention-to-treat, with sensitivity analyses to explore the effect of dropout. Due to the exploratory nature of the study no multiplicity adjustment will be made to p-values for secondary analyses, though results will be interpreted with caution if the primary endpoint does not achieve significance.

It will only be possible to measure sTfR for every study participant after enrolment and thus a separate analysis will be performed to analyse the effect of Ferinject® in patients with sTfR > 28.1 nmol/l. Additionally, on recruitment of the 20th, 40th and 60th patient, serum samples will be analysed to establish the number of patients enrolled with sTfR > 28.1 nmol/l and an additional number of patients will be recruited to achieve 60 enrolled iron-deficient patients.

Data from all centres will be pooled and analysed at Hammersmith. Due to the small sample sizes in each centre, the assessment of consistency of results amongst the centres will be made on an informal basis.

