Patients with IPAH and iron-deficiency, who have been stable on their current therapy for the preceding 1 month, will be treated with 1000 mg or 15 mg/kg (whichever is the smaller) Ferinject® in line with the Summary of Product Characteristics (SmPC) and clinical experience with the product. Soluble transferrin receptor (sTfR) is the best measure of iron deficiency in inflammatory diseases such as IPAH ( $>28.1 \text{ nmol/l}$ ). Where available, sTfR levels will be used as the screening tool to assess iron deficiency and inclusion in to the study. But as it is not routinely available at all participating centres, iron deficiency will also be defined by standard laboratory measures of ferritin  $< 37 \text{ ug/l}$ , iron  $< 10.3 \text{ umol/l}$  or transferrin saturations  $< 16.4\%$ . Using these criteria, modelling of data from our previous work (1) show that 83% of patients will have raised sTfR levels  $> 28.1 \text{ nmol/l}$ .

A formula exists to guide the amount of iron replacement required to render patients with anaemia iron-replete. This is based on the difference between current and target haemoglobin. In IPAH, this formula is likely to be inappropriate since the target haemoglobin is not known as patients may be hypoxaemic and thus require higher levels of haemoglobin. Indeed, many patients with iron deficiency have normal haemoglobin levels, but increased circulating EPO levels, implying an ongoing drive to increased red cell mass. Patients in the FERRIC-HF trial of iron supplementation in congestive heart failure were defined as having iron deficiency if ferritin was less than 100 ug/l or between 100 and 300 ug/l with transferrin saturations  $< 20\%$  (6). By 4 and 16 weeks,  $781 \pm 94$  and  $1269 \pm 297$  mg iron sucrose had been given to the non-anaemic group ( $\text{Hb} > 12.5 \text{ g/dl}$ ) and  $1051 \pm 219$  and  $1583 \pm 366$  mg had been given to the anaemic group. Iron sucrose can be given in doses up to 200mg, whereas Ferinject® can be given in doses up to 1000mg due their differing pharmacokinetics. We will give a single 1000mg (or 15 mg/kg) dose to answer whether this simple strategy is of benefit and well-tolerated. Experience from Viethen et al (2013) and Ruiter et al (2015) in a total of 35 patients indicate that this is well tolerated and does not lead to iron overload (4,5). Using full iron profiling we will be able to determine how long this dose maintains iron repletion.

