### **3.2. Secondary outcomes:**

The secondary outcomes will be measured by capturing other data, particularly exercise parameters and NT-pro-BNP data.

A summary of the measurements that will be made is as follows:

- Incremental bicycle cardiopulmonary exercise testing – measurements will include peak VO2 (ml/min/kg), VO2 at metabolic threshold, VE/VCO2 slope, VE/VCO2 equivalents at metabolic threshold, VO2/WR slope and O2 pulse. Details are described in the Study Procedures Manual (SPM).
- VO2 at the end of endurance bicycle cardiopulmonary exercise testing at 80% peak work rate determined from the incremental exercise test
- Gas exchange at 3 minutes after the start of the work phase of an endurance exercise test at 80% peak work rate determined from the incremental exercise test
- Iron indices – serum iron, transferrin saturations, ferritin, soluble transferrin receptor, RDW, EPO, and UIBC
- 6 minute walk distance and Borg dyspnoea scale
- WHO functional class
- NT-proBNP
- Quality of life (CAMPHOR questionnaire) and the self-reported Patient Global Assessment
- Safety - the occurrence of adverse events
- Cardiac MRI - right ventricular volumes, mass, ejection fraction, stroke volume and diastolic function. Details are described in the SPM.

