#### **4.2. Discussion of study design**

Patients will be randomised 1:1 to Ferinject® or saline, with a 6-minute walk test, cardiac MRI and incremental and endurance cardiopulmonary exercise tests to measure changes in cardiopulmonary performance. Patients will then receive the alternative treatment and 6-minute walk test and endurance and incremental cardiopulmonary exercise testing repeated after a further 12 weeks (Figures 1). This crossover design maximises the data available on exercise testing at 12 weeks post-iron for analysis.

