#### **4.3.5. Replacement policy**

Patients who are prematurely discontinued from the study will not be replaced.

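### Section 10's 80% power for 1.94 ml/min/kg in peak VO2 fits only one 10% loss; over the two 12-week periods of a crossover pair, 60 enrolled give about 75%, or 80% for about 2.05.

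*Protocol*

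**What the plan says.** The Section 10 sentence begins "if a 12-weekly drop-out rate of 10% and standard deviation of 5 ml/min/kg for peak" VO2 and continues "we would have 80% power to detect a mean change of 1.94 ml/min/kg at a significance level of alpha=0.05 using a paired analysis". It then compares this with a 2.2 ml difference seen in an iron trial in heart failure. The preceding paragraphs give a sample size of 60 and a two-sided alternative. The number of pairs is not stated, nor whether 5 ml/min/kg is the SD of a within-patient difference or a between-patient SD.

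Four other statements bear on it:

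- Section 4.2: after crossing over, patients have "endurance and incremental cardiopulmonary exercise testing repeated after a further 12 weeks", so the second half of each pair is measured at week 24.
- Section 4.3.5: "Patients who are prematurely discontinued from the study will not be replaced".
- Section 10: the endpoints are to be analysed "using linear mixed models for analysis of the crossover data".
- Section 10: after sTfR testing of those recruited, "an additional number of patients will be recruited to achieve 60 enrolled iron-deficient patients". Section 1 says modelling of earlier data "show that 83% of patients will have raised sTfR levels" above 28.1 nmol/l.

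Peak VO2 comes under "Incremental bicycle cardiopulmonary exercise testing" in Section 3.2 and is a secondary outcome. The primary outcome in Section 3.1 is endurance time.

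**The concern.** The drop-out assumption is a rate per 12 weeks, while the analysis is paired across two 12-week periods. If the rate is applied once, the calculation counts patients who reach week 12 and treats them all as complete pairs, although some leave before week 24. The printed power would then be higher than the protocol's own inputs support.

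This is the only quantified power statement in Section 10. No SD, effect or power is given there for endurance time, so a reader judging the trial's sensitivity has only this sentence. Section 1 also says that a favourable result would be used to power a Phase 3 study, and a one-period drop-out allowance could be carried into that calculation.

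**Working it through.** **Inputs.** From Section 10: N = 60, drop-out 10% per 12 weeks, SD 5 ml/min/kg, two-sided alpha 0.05, paired analysis, 80% power, difference 1.94. From Sections 4.2 and 4.3.5: two 12-week periods per pair, and no replacement.

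**Formula.** For n pairs, difference d and SD of the paired difference s, the test has n − 1 degrees of freedom and noncentrality (d/s)√n. Power is the probability that this noncentral t exceeds the 97.5% point of the central t. The detectable difference is the d at which power is 0.80.

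**Reproducing 1.94 (s = 5).**

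| Pairs | Basis | Power at 1.94 | Detectable at 80% |
|---|---|---|---|
| 60 | no loss | 84.0% | 1.84 |
| 54 | 60 × 0.9 | 79.9% | 1.942 |
| 48.6 | 60 × 0.9 × 0.9 | 75.5% | 2.05 |

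Only the single-loss row gives the printed figure. The normal approximation, (1.960 + 0.842) × 5/√n, gives 1.906 with 54 pairs and 2.009 with 48.6.

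**Applying the stated rate to both periods.** Whole numbers either side of 48.6 give:

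- 48 pairs: power at 1.94 is 74.9%, detectable difference 2.06.
- 49 pairs: power at 1.94 is 75.8%, detectable difference 2.04.

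Power at the 2.2 comparator with 48.6 pairs is 85.2%. Using n − 2 degrees of freedom, as a two-sequence crossover analysis would, leaves 75.5% and 2.05.

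**Mixed model.** Of the 54 patients reaching week 12, 54 × 0.1 = 5.4 leave before week 24 and contribute period 1 only. With within-patient correlation r, generalised least squares gives an effective number of pairs of 48.6 + 5.4 × (1 − r)/2. The protocol gives no r, so 0.3 to 0.8 is assumed:

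- r = 0.3: 50.5 pairs, power 77.1%, detectable 2.01.
- r = 0.8: 49.1 pairs, power 76.0%, detectable 2.04.

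**Before-versus-after-iron reading.** Iron-first patients need one period (30 × 0.9 = 27) and placebo-first patients need two (30 × 0.81 = 24.3), giving 51.3 pairs. Power at 1.94 is 77.8% and the detectable difference is 1.99; by normal approximation they are 79.4% and 1.956.

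**SD 5 as a between-patient SD.** The SD of the difference is then 5√(2(1 − r)). Power at 1.94:

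| r (assumed) | 54 pairs | 48.6 pairs |
|---|---|---|
| 0 | 50.8% | 46.6% |
| 0.3 | 65.8% | 61.0% |
| 0.5 | 79.9% | 75.5% |
| 0.7 | 95.1% | 92.8% |

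The omitted loss costs 2 to 5 points at every value. At r = 0.5 the SD of the difference is exactly 5, so the two readings coincide.

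**sTfR top-up.** If 83% of those enrolled qualify, 60/0.83 = 72.3 are enrolled and 72.3 × 0.81 = 58.6 pairs remain. Power at 1.94 is 83.1% in all patients and the detectable difference is 1.86. The 60 sTfR-positive patients still yield 48.6 pairs and 75.5%.

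**The case against.** The single loss is inferred. The protocol never states 54 pairs, a formula or the meaning of the SD, and by normal approximation 52 pairs also give 1.943. The before-versus-after-iron reading has some support in the text: Section 10 speaks of a mean change, and Section 4.2 justifies the crossover by the amount of data 12 weeks after iron. That reading does apply the drop-out rate over two periods where needed, and by normal approximation it comes within 0.02 of 1.94. It still does not reproduce the printed figure, and it is not the iron-versus-placebo comparison that a crossover is analysed for. The 54-pair t-test remains the best fit, but the inference should be acknowledged.

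The practical shortfall may also be smaller than the headline suggests. The planned mixed model recovers 0.5 to 1.6 points, which leaves power short of 80%. The top-up, if 83% qualify, lifts power in all patients above 80%. However, the power sentence rests on 60 and makes no use of the top-up, and the separate sTfR-positive analysis stays at 75.5%.

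Finally, power did not determine the sample size, and the endpoint is secondary. Both points stand and limit the importance of the error. The lack of any sensitivity figure for endurance time is a separate matter and adds no weight to this one.

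**Conclusion.** The stated power does not follow from the protocol's own inputs. With 60 enrolled, 10% lost in each of two 12-week periods, a paired t-test on complete pairs and 5 ml/min/kg as the SD of the difference, power at 1.94 is about 75% rather than 80%. The difference detectable at 80% is about 2.05 rather than 1.94. Allowing for the mixed model, power is 76 to 77%.

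This is a minor numerical correction. The corrected detectable difference is still below the 2.2 ml comparator, and no design element changes. What remains open is the meaning of the SD: if it is between-patient, absolute power depends on a correlation that the protocol does not give, although the direction of the error is the same.

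**What to change.** Replace the power sentence in Section 10 with one that states the number of pairs, for example:

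*With 60 enrolled and 10% drop-out in each 12-week period, about 48 to 49 patients complete both periods. Taking 5 ml/min/kg as the SD of the within-patient difference, this gives about 75% power for a difference of 1.94 ml/min/kg in peak VO2, a secondary endpoint, or 80% power for about 2.05, before any sTfR top-up.*

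The authors should first confirm what the SD of 5 refers to. If it is between-patient, they should add the correlation they assume and recompute.

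Two additions are optional. One is the top-up scenario: about 72 enrolled and about 83% power in all patients, against about 75% in the 60 sTfR-positive. The other is the same sensitivity in standardised units, 2.05/5 = 0.41 SD of the paired difference, which could also be quoted for endurance time.

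The cost is one restated sentence and one confirmed input. The quoted figure becomes slightly less favourable, and enrolment does not change.

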## **11. ADMINISTRATIVE AND LEGAL CONSIDERATIONS**

### **11.1. General Legal Requirements**

This trial will adhere to the principles outlined in the Medicines for Human Use (Clinical Trials) Regulations 2004 (SI 2004/1031 and its amendments) or any legislation that supersedes these regulations and the International Conference on Harmonisation Good Clinical Practice (ICH GCP) guidelines. It will be conducted in compliance with the protocol, the Data Protection Act and other regulatory requirements as appropriate.

### **11.2. Ethics Committee/RA approvals**

Approval must be obtained from a Research Ethics Committee (REC) and the Regulatory Authority (RA) before starting the study and must be documented in a dated letter to the investigator clearly identifying the trial, the documents reviews, and the date of the approval.

A list of the Ethics Committee members must be provided. If any study staff were present, it must be clear that none of these persons voted.

Modifications made to the protocol after receipt of the REC/RA approval must also be submitted as amendments by the investigator to the REC/RA in accordance with local procedures and regulations.

### **11.3. Informed consent**

It is the Investigator's responsibility to explain to each subject the study procedures, potential benefits and hazards of trial participation, the right to withdraw from the study at any time, and to obtain written informed consent prior to any study-specific procedures. The original copy of the signed and dated Informed Consent Form must be filed in the Investigator Site File. The subject, the subject's legally authorised representative, or both will be given a copy of the signed and dated Informed Consent Form. A copy will also be placed in the subject's medical hospital notes.

### **11.4. Patient confidentiality**

The Investigators affirm and uphold the principle of the subject's right to protection against invasion of privacy. Personal health data will be kept confidential.

On CRFs or other documents, subjects will be identified by their initials and a subject number only. However, each Investigator will keep in his/her file a *Subject Identification List*. With respect to the processing of data, every subject has to agree with this in writing. This agreement should be documented together with the written informed consent for trial participation.

#### **11.5. Protocol Amendments**

Any changes in the protocol will require a formal amendment. Such amendments will be agreed upon and approved in writing by the Investigator. Amendments to the protocol will be submitted to the relevant authorities and the REC for approval prior to implementation.

Administrative changes which have no significant impact on the medical or scientific validity of the study will be documented in a statement. The REC will be notified of administrative changes, if applicable.

#### **11.6. Premature Termination of the Trial**

The Chief Investigator reserves the right to terminate the trial for well-documented reasons. Instructions will be provided in a separate document should it be determined that assessments beyond those defined by the protocol are required.

Further recruitment of subjects will not take place under the following conditions:

- Premature termination of the trial.
- Drug-related events, i.e. SUSARs, emerging adverse effects that are serious and the risk/benefit ratio is unacceptable.
- Procedure-related events, i.e., the recruitment rate is too low or the number of dropouts for administrative reasons is too high.

#### **11.7. Sponsor**

Imperial College Academic Health Science Centre will act as the main Sponsor for this study. Delegated responsibilities will be assigned to the NHS trusts taking part in this study.

#### **11.8. Indemnity**

Imperial College holds Public Liability ("negligent harm") and Clinical Trial ("non-negligent harm") insurance policies which apply to this trial.

#### **11.9. Record Retention**

The PI must retain all study records by the applicable regulations in a secure and safe facility. The PI/institution must take measures to prevent accidental or premature destruction of essential documents, that is, documents that individually and collectively permit evaluation of the conduct of a study and the quality of the data produced, including paper copies of study records (e.g. subject charts) as well as any original source documents that are electronic as required by applicable regulatory requirements.

The PI/institution should retain subject identifiers for at least 15 years after the completion or discontinuation of the study. Subject files and other source data must be kept for the maximum period of time permitted by the hospital, institution or private practice, but not less than 15 years. These documents should be retained for a longer period, however, if required by the applicable

regulatory requirements. It is the responsibility of the PI to inform the institution as to when these documents no longer need to be retained.

If an Investigator moves, withdraws from an investigation, retires, requests to move records to another location or to assign these records to another party or (e.g. other Investigator) who will accept the responsibility, written notice of this transfer must be made to and agreed upon by each party.

#### **11.11. Publications**

Publication of the results of the study, whether in whole or in part, shall be within the responsibility of the Investigator(s).

#### **11.12. Audits and Inspections**

To ensure compliance with GCP and all applicable regulatory requirements, the sponsor may conduct a quality assurance audit in accordance with their local internal procedures.

Audits and/or inspections may also be carried out by local authorities, or authorities to which information on this trial has been submitted. All documents pertinent to the trial must be made available for such inspection after an adequate announcement.

**Table 1. Visit and Assessment Schedule**

Assessment	Screening # ≤ 28 days before week 0 visit	Week 0 Baseline/ randomisation Visit 1 §	Week 2 (+/- 3 days) Telephone Visit 2	Week 12 (+/- 3 days) Visit 3	Week 14 (+/- 3 days) Telephone Visit 4	Week 24 (+/- 3 days) Visit 5
Written informed consent	X					
Medical history (incl. demographics)	X					
Physical examination	X	X		X		X
Concomitant medication	X	X	X	X	X	X
Modified NYHA (WHO) Functional Class	X		X	X	X	X
Vital signs	X	X		X		X
ECG		X		X		X
6MWT and Borg Dyspnoea Score	X			X		X
CAMPHOR Questionnaire		X		X		X
Patient Global Assessment (PGA)			X	X	X	X
Routine laboratory assessments (e.g. iron status)	X	X		X		X
Research blood sampling		X		X		X
Serum pregnancy testing (if applicable)	X			X		X
Incremental Cardiopulmonary Exercise Test		X		X		X
Endurance Cardiopulmonary Exercise Test		X		X		X
Administration of study drug or placebo		X		X		
Adverse events		X	X	X	X	X
Cardiac MRI*		X		X		X

Visit 2 & 4 (Week 2 & 14) will be done by telephone call.

#; Iron status and IPAH status will be determined from routine clinical care records.

§; Screening procedures can be combined with Visit 1 wherever convenient for patient and where data from routine clinical visits are not available.

\*; Additional exploratory assessments, where research facility for MRI available for this protocol
